FIGURE 2: Fundus changes following intravitreal injection of autologous CD34+ stem cells in an eye with central retinal vascular occlusion. Fundus photography of an eye with persistent vision loss from a combined central retinal vein and artery occlusion 9 months earlier (left). Improvement in vision and fundus exam noted 3 months after intravitreal injection of autologous bone marrow CD34+ cells (right).²³ By selecting out the CD34+ cells from bone marrow mononuclear cell fraction of the bone marrow aspirate, a higher concentration of these effector cells can be administered locally, potentially enhancing the therapeutic effect.⁴⁻⁹ The study investigators have initiated a phase 1 study exploring the safety and feasibility of intravitreal injection of autologous CD34+ cells from bone marrow as potential treatment for ischemic or degenerative retinal conditions. This is based on an IND cleared by the Food and Drug Administration (FDA) and cross-referenced for the current IND (i.e., IND #13307). A total of 9 participants have enrolled in this study. The results of the first six participants who enrolled and completed the study have been published.²³ No ocular or systemic safety issues were noted in any enrolled participants during the six-month follow-up of the study and during the extended two-year follow-up as part of standard of care.²³ No feasibility issues were noted. The bone marrow aspiration was well tolerated under local anesthesia and a desired number of CD34+ cells could be obtained for intravitreal injection from a single bone marrow aspirate in each participant. Among the first six study eyes, the eye with retinal ischemia from a combined central retinal vein and artery occlusion appeared to have the most dramatic improvement in vision and fundus findings following intravitreal cell therapy (Figure 2).²³ Some improvement in the retinal microvascular abnormalities on fluorescein angiography and fundus photography could be observed within three months following the study treatment.

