The participants will have a complete eye examination 1 day and 1 week (±2 days) after their first study treatment (either cell or sham) by the unmasked treating ophthalmologist. Thereafter, a follow-up examination 1 month (±7 days), 3 months (±14 days) and 6 months (±30 days) will be conducted by the masked examining ophthalmologist. At month 6, the participant will receive the second study treatment (either cellular or sham therapy which is the opposite of what they originally received) by the unmasked treating ophthalmologist. Prior to the receipt of the second study treatment, the participant will meet with the study hematologist to review the aspiration procedure. Similar to the first consult, the hematologist will review the participant's medical history, concomitant medications, and blood work (including CBC) to ensure that the participant is still a good candidate for bone marrow aspiration. Any abnormal lab work and review of systems will be reviewed by the hematologist to determine whether it would impact the outcome of the bone marrow aspiration procedure and continued treatment in the study. In addition, females of child-bearing potential must have a negative pregnancy test within 2 weeks of the second study treatment. Similar to what occurs for the first treatment, the study team will meet with the participant on the morning of the study procedure to ensure there are no new contraindications to proceeding with study treatment that day.

Following the study injection, the unmasked treating ophthalmologist will conduct a follow-up exam 1 day and 1 week after this second study treatment. The masked examining ophthalmologist will conduct an exam 1 month, 3 months (\pm 14 days) and 6 months (\pm 30 days) after the second study treatment (i.e., at approximately 7, 9 and 12 months after the first study treatment).

The bone marrow aspiration wound site will be inspected visually for infection at the 1 day and 1 week (±2 days) post-procedure examinations by the unmasked treating ophthalmologist.

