7.5 Study Assessments and Monitoring of Study Progress

All participants will be examined 1 day, 1 week (± 2 days), 1 month (± 7 days), 3 months (± 14 days), and 6 months (± 30 days) following each of the two therapies (sham or cellular). These examinations will evaluate for any ocular adverse effect associated with the therapy and to gauge for any possible benefit. The details of the diagnostic tests to be performed are as outlined in **TABLE 2** for the 2 study groups. Participants will follow the same follow-up schedule regardless of which study group they are assigned.

During the first week after cellular therapy, the bone marrow aspiration site will be visually inspected for evidence of infection or bleeding. To maintain masking, a similar post-procedure examination will be performed for the participants receiving sham therapy.

The study progress will be monitored by the Study Chair/PI and the DCC. After every six months or on a schedule approved by the DSMC, a summary of study enrollment, study retention, adverse events, and study outcomes as appropriate will be presented and reviewed by the DSMC. An annual report of the study progress will be submitted to the local regulatory agencies and the FDA.

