7.6 Participant Discontinuation/Replacement

Participants have a right to withdraw from the study at any time and for any reason. The Enrollment Center may request to withdraw a participant because of protocol deviation, administrative reasons, safety concerns, inadequate number of viable nucleated CD34+ cells harvested for intravitreal injection (where the cell count is based on the Miltenyi CliniMACS cell sorting process) or any other valid and ethical reasons. A study termination form will be completed citing the reason for the termination. In the event that a participant is terminated from the study

after randomization and prior to receipt of treatment (cellular or sham) at the Treatment 1 visit regardless of the reason, an additional participant will be accrued as a replacement. In the event that a participant receives the first treatment but opts not to receive the second treatment, an additional participant will be accrued as a replacement, but the original participant will be encouraged to return for all study visits to ensure the participant's safety is not compromised. The replacement participant will receive both treatments and will be followed for 12 months, the same as any other participant enrolled in the study. If a participant is terminated or withdraws from the study following the receipt of the second treatment, the participant will again be encouraged to return for all study visits for safety monitoring but will not be replaced. A maximum of one participant may be replaced, regardless of timing of withdrawal. If a participant terminates the study due to having less than 800,000 viable nucleated CD34+ cells (where the cell count is based on the Miltenyi CliniMACS cell sorting process) in the final product for intravitreal injection, the participant will have the option to receive the harvested cells as part of the on-going open-label pilot study provided that the harvested cells pass the release criteria for quality and sterility.

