8.5 Naming and Grading of Adverse Events

Each adverse event will be graded for severity based on the severity grading outlined below:

- Grade 1 (Mild) An AE that is easily tolerated by the participant, causing minimal discomfort and not interfering with everyday activities.
- Grade 2 (Moderate) An AE that is sufficiently discomforting to interfere with normal everyday activities.
- Grade 3 (Severe) An AE that prevents normal, everyday activities. In adults, such an AE would, for example, prevent attendance at work/school and would necessitate the administration of corrective therapy.

All adverse events will be followed by the Investigator until resolution or up to one month after study termination or until the study participant is lost to follow-up. The Investigator will treat or observe participants with adverse events as appropriate for standard of care and follow the participants at regular intervals until resolution or stabilization of the adverse event.

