3.6 Participant Discontinuation / Replacement

In the event that a participant is terminated from the study after randomization and prior to receipt of treatment (cellular or sham) at the Treatment 1 visit regardless of the reason, an additional participant will be accrued as a replacement. In the event that a participant receives the first treatment but opts not to receive the second treatment, an additional participant will be accrued as a replacement, but the original participant will be encouraged to return for all study visits to ensure the participant's safety is not compromised. The replacement participant will receive both treatments and will be followed for 12 months, the same as any other participant enrolled in the study. If a participant is terminated or withdraws from the study following the receipt of the second treatment, the participant will again be encouraged to return for all study visits for safety monitoring but will not be replaced. A maximum of one participant may be replaced, regardless of timing of withdrawal.

Table 2 contains these follow-up and replacement decisions for each scenario.

Scenario		Original Participant Follow-up	Included in ITT?	Replacement Decision		
1	Participant terminates/withdraws after randomization prior to cellular/sham therapy on Day 0 (includes inadequate sample following bone marrow aspiration)	No further assessments performed; participant only followed to close-out any AEs.	No	Additional patient will be accrued as a replacement		
2	Participant receives 1 st treatment but withdraws during Period 1 / refuses further treatment	Participant encouraged to follow visit schedule at least through Month 6 or longer (for safety monitoring)	Yes	Additional participant will be accrued as a replacement (up to 1 time)		
3	Participant has inadequate sample following bone marrow aspiration (period 2)	Participant cannot receive 2 nd treatment; is necessarily unmasked	Yes	Additional participant will be accrued as a replacement (up to 1 time)		
4	Participant receives 2 nd treatment but withdraws during Period 2	Participant encouraged to follow visit schedule through Month 12 (for safety monitoring)	Yes	No replacement		

Table 2: Participant Follow-up and Replacement Decisions

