7.1.2 Feasibility

The number and percent of study participants undergoing successful bone marrow aspiration will be summarized. The mean and range of volume of bone marrow aspirate, number of CD34+ cells isolated and number of CD34+ cells injected intravitreally will be described to determine whether a desired number of stem cells can be isolated from bone marrow aspiration without sedation in an outpatient setting. Any participant who did not tolerate the bone marrow aspiration without sedation without sedation and any unsuccessful bone marrow aspiration attempt will be recorded.

Other pre- and post-release analysis parameters such as percent yield of the CD34+ isolation will also be described.

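### SAP section 11 runs every safety output on the ITT set, so a participant aspirated at Treatment 1 but never injected would drop out of the aspiration-event and AE tables that SAP 4.3 and 7.1.1 say should include everyone

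*SAP*

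**What the plan says.** **Populations.** SAP 4.1.2 limits the (modified) ITT set to randomized participants who were given the first injection. SAP 4.1.3 defines the safety population as everyone who consented, and SAP 4.3 assigns safety analyses to it. SAP 7.1.1 draws on adverse events from all participants and promises a summary of aspiration-related events and listings of pre-treatment AEs.

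**Outputs.** SAP section 11 says its population column is the set used to produce each output. Every row under primary and secondary safety reads ITT.

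**The participant in question.** SAP Table 2 (section 3.6), scenario 1, covers anyone who leaves after randomization and before Day 0 therapy, and the row "includes inadequate sample following bone marrow aspiration". The follow-up entry is "No further assessments performed; participant only followed to close-out any AEs", and the ITT entry is No. Scenario 3, an inadequate harvest in period 2, is marked Yes for ITT.

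**Site checks and safeguards.**
- Protocol 6.1.5: "The bone marrow aspiration wound site will be inspected visually for infection at the 1 day and 1 week (±2 days) post-procedure examinations".
- Protocol 7.5: "During the first week after cellular therapy, the bone marrow aspiration site will be visually inspected for evidence of infection or bleeding".
- Protocol 8.5: AEs are "followed by the Investigator until resolution or up to one month after study termination".
- Protocol 7.6, for a yield below 800,000 viable cells: "the participant will have the option to receive the harvested cells as part of the on-going open-label pilot study", if the cells meet release criteria.
- SAP 7.1.2: "any unsuccessful bone marrow aspiration attempt will be recorded".

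**The concern.** Bone marrow aspiration, with up to four bone punctures (Protocol 6.1.5), is an invasive part of the therapy whose safety is the primary objective. Someone who had it but was not injected has been exposed to that risk. The SAP's general rules would count this person, but the output list would not. A programmer working from section 11 would leave out any site bleed, infection or SAE in this person from the listed outputs, including those meant to show aspiration events. At stake is a selective gap in the primary safety outcome of a trial with about 10 participants per arm, where a single event changes the picture. A secondary question is whether anyone would actively look for such an event once scenario 1 applies.

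**Working it through.** The documents give no figure to reproduce here. The check compares definitions and then sizes the gap.

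**1. Row count in section 11.** The safety block has 28 rows. Three titles are printed twice (the two vision-related summaries and the aspiration summary), which leaves 28 − 3 = 25 distinct titles. All are labelled ITT and none Safety. The feasibility and clotting rows carry the same label.

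**2. Following the participant through the plan.**
- Aspiration done, no injection: outside ITT under both SAP 4.1.2 and Table 2.
- Inside the safety population under 4.1.3, and so inside safety analyses under 4.3 and 7.1.1.
- In no section 11 safety output.
- The same failure at Treatment 2 stays in ITT, so the gap is confined to Treatment 1.

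**3. Before or after treatment?** SAP 4.2.5 starts post-treatment on the day of first treatment, and Protocol 6.1.5 counts aspiration as part of cell therapy, so an aspiration event could be post-treatment. Table 2, however, places this participant before therapy. If the event counts as pre-treatment, the only matching section 11 row is a listing of serious events, again ITT. A non-serious aspiration event therefore has no listed output on either reading.

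**4. Which arm?** An inadequate harvest at Treatment 1 needs a real aspiration, so it can occur only in the immediate-cell arm. Withdrawal between aspiration and injection can occur in either arm.

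**5. Chance of an omitted event.** Inputs: 20 participants randomized 1:1 (SAP 3.2), so about 10 real aspirations at Treatment 1. The failure rate r and the aspiration-event rate e are assumptions, because the documents give neither. With independence, P(at least one omission) = 1 − (1 − r·e)^10.

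| r | e = 10% | e = 50% |
|---|---|---|
| 1% | 1 − 0.999^10 = 1% | 1 − 0.995^10 = 5% |
| 5% | 1 − 0.995^10 = 5% | 1 − 0.975^10 = 22% |
| 10% | 1 − 0.99^10 = 10% | 1 − 0.95^10 = 40% |

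The chance of a failed harvest alone, 1 − (1 − r)^10, is 10%, 40% or 65%. The table covers failed harvests only. Withdrawals between aspiration and injection would add to it by an unknown amount.

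**6. What the pilot says about r.** Protocol 4.0 reports that "a desired number of CD34+ cells could be obtained for intravitreal injection from a single bone marrow aspirate in each participant". Read as 0 failures in 6 published participants, the one-sided 95% upper limit is 1 − 0.05^(1/6) = 39%. Read as 0 in 9 enrolled, it is 1 − 0.05^(1/9) = 28%. The pilot is reassuring but does not rule out any rate in the table.

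**7. Illustration, if it happens.** Suppose one failed harvest has an aspiration event and nobody else does. For real aspirations in Period 1, the report would show 0/10 (one-sided 95% Clopper-Pearson upper limit 26%) instead of 1/11 (36%). Over both periods it would show 0/20 (14%) instead of 1/21 (21%).

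**The case against.** The strongest reply is that the SAP's method text already covers this participant. SAP 7.1.1 uses events from all participants, summarizes aspiration events and lists pre-treatment AEs; Protocol 7.8.2.1 says much the same. On that view section 11 is only a mislabelled list. This stands in part: a reader might infer that the SAP has no plan to report these events, and that would be wrong. But section 11 says its column governs how outputs are produced. SAP 4.3 lets later sub-sections note deviations, yet section 11 does not present ITT as one. Two instructions conflict, and the one closest to programming omits the participant.

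A reader might also infer that the omission falls only on the immediate-cell arm. That is true of failed harvests, but a sham participant who leaves between sham aspiration and sham injection is excluded too.

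On follow-up, a reader might infer that the participant is abandoned after a failed harvest. The documents do not support that. Protocol 7.6 orders no such stop, the site check in Protocol 6.1.5 can be read to cover any aspiration, AEs are followed for up to a month after termination, site-care instructions are given, and the open-label pilot is an option. What is left is the lack of a clearly stated active check for a new event. That part may also come too late to alter care: SAP version 1.0 is dated 2 April 2024, and 42 planned months of recruitment counted from August 2020, when enrolment was already under way, end in February 2024. The actual end of enrolment is not given.

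Finally, safety reporting is descriptive and no decision rule uses the limits in step 7. That is correct and keeps the point small.

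**Conclusion.** The conflict between SAP 4.1.3, 4.3 and 7.1.1 on one side and section 11 on the other is real. Followed literally, section 11 removes from every listed safety output the aspiration events of anyone aspirated but not injected at Treatment 1. The likely effect is small, because an omission needs both a participant who stops at that point and an aspiration event. For failed harvests the chance is about 1% to 10% with an assumed 10% event rate and about 5% to 40% with an assumed 50% rate, over assumed failure rates of 1% to 10%. The 10%, 40% and 65% in step 5 are chances of a failed harvest and should not be read as chances of a lost event. Nothing changes if no participant stopped between aspiration and injection. The follow-up question is secondary: Table 2 and the protocol do not say clearly whether the site checks are kept, and the gap is limited to active detection of new events. This is a low-severity correction, worth making because it is cheap and concerns the primary safety outcome.

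**What to change.** 1. In section 11, produce the post-treatment AE, SAE and aspiration outputs on all randomized participants who began a real or sham aspiration, by procedure received. Applying the all-consented set to these tables would add screen failures, who have no arm, to by-treatment denominators. Adjust SAP 4.3 to match.
2. Keep the all-consented population for the pre-treatment AE listing promised in SAP 7.1.1, and name that listing in section 11.
3. In SAP 4.2.5, state that events from the start of the first real or sham aspiration count as post-treatment.
4. In Table 2, split scenario 1 into no procedure performed and aspiration performed without injection. For the second, state that the day 1 and week 1 site checks and AE collection are kept. Unmasked staff already conduct those visits, so masking is not affected.

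The cost is a set of population labels, one table row and a sentence or two of definition. If anyone is still to be treated, it adds at most two already scheduled visits for a few participants.

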4.0 GENERAL ANALYSIS POPULATIONS, DEFINITIONS AND CONVENTIONS

4.1 Analysis Populations

4.1.1 Screened Population

The screened population consists of candidates that meet basic study eligibility criteria who signed the written informed consent (IC) at the initiation of the screening process and were enrolled into segment A.

4.1.2 Intent-to-Treat Population

The (modified) intent-to-treat population consists of all participants who were randomized and received the first injection (cellular or sham). For analyses, these participants will be analyzed in the arm to which they were randomized.

4.1.3 Safety Population

The safety population includes all participants who completed written informed consent.

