4.2.5 Post-treatment AEs

Post-treatment AEs are events that occur on or after the day of the first treatment (cellular or sham).

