4.3 Tables, Figures and Listings Conventions

Safety analyses will be summarized for the safety population. All other analyses described in this document will be done for the ITT population and summarized by randomized treatment group and overall. For all summaries of ITT population, participants will be analyzed according to the treatment arm to which they were randomized regardless of the subsequent sequence of events regarding study drug exposure.

Continuous variables will be summarized using the following descriptive statistics: n (non-missing sample size), mean, standard deviation, percentiles (median, maximum, and minimum). Categorical variables will be summarized in terms of frequencies and/or percentages.

Any deviations from the above general conventions will be noted in the subsequent sub-sections.

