11.0 LIST OF PROPOSED TABLES, LISTINGS AND FIGURES

The below listing provides the title of the tables, listings, and figures (TLFs) that will be provided, along with the analysis population used to generate each TLF. See the accompanying "Statistical Analysis Plan Shells" document for the table, listing and figure shells that show the planned layout of the TLFs.

Section	Title	Population
Enrollment,	CONSORT Diagram	Prescreened
Participant Disposition,	Proposed vs Actual Randomizations	Screened
and Follow-up	Figure of Proposed vs Actual Randomizations	Screened
	Summary of Screen Failures	Screened
	Summary of Participant Disposition by Treatment Arm	ITT
	Summary of Attendance at Follow-up Visits by Treatment Arm	ITT
	Summary of Early Study Terminations by Treatment Arm	ITT
	Summary of Reasons for Missed Visits	ITT
Participant	Summary of Baseline Demographics by Treatment Arm	ITT
at Baseline	Summary of Baseline Medical History by Treatment Arm	ITT
	Summary of Baseline Ocular History in Study Eye by Treatment Arm	ITT
	Summary of Baseline Ocular History in Fellow Eye by Treatment Arm	ITT
Patient Profiles	Patient Profiles	ITT
Primary Outcome –	Summary of Post-treatment Adverse Events for Treatment Period 1 by Treatment	ITT
Primary and Secondary Safety	Summary of Post-treatment Adverse Events in the Study Eye for Treatment Period 1 by Treatment	ITT
	Summary of Post-treatment Adverse Events for Treatment Period 2 by Treatment	ITT
	Summary of Post-treatment Adverse Events in the Study Eye for Treatment Period 2 by Treatment	ITT
	Listing of Post-treatment Serious Adverse Events by Treatment Arm	ITT
	Summary of Post-treatment MedDRA Coded Adverse Events in Study Eye for Treatment Period 1 by Treatment	ITT
	Summary of Post-treatment MedDRA Coded Adverse Events in Study Eye for Treatment Period 2 by Treatment	ITT

Section	Title	Population
	Summary of Post-treatment MedDRA Coded Adverse Events in Fellow Eye for Treatment Period 1 by Treatment	ITT
	Summary of Post-treatment MedDRA Coded Adverse Events in Fellow Eye for Treatment Period 2 by Treatment	ITT
	Summary of Post-treatment MedDRA Coded Non-ocular Adverse Events for Treatment Period 1 by Treatment	ITT
Summary of Post-treatment MedDRA Coded Non-ocular Adverse Events for Treatment Period 2 by Treatment		ITT
	Summary of Post-treatment MedDRA Coded Serious Adverse Events in Treatment Period 1 by Treatment	ITT
	Summary of Post-treatment MedDRA Coded Serious Adverse Events in Treatment Period 2 by Treatment	ITT

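### The SAP text assigns safety analyses to everyone who consented, but Section 11 runs every safety output on ITT, which leaves out anyone aspirated on Day 0 but not injected

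*SAP*

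**What the plan says.** SAP 4.1.3 defines the safety set: "The safety population includes all participants who completed written informed consent". Neither randomisation nor any procedure is required. SAP 4.3 then says "Safety analyses will be summarized for the safety population" and sends all other analyses to ITT.

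SAP 4.1.2 limits the (modified) ITT set to people who were randomised and got a first injection, whether cells or sham, and adds that "these participants will be analyzed in the arm to which they were randomized". SAP 4.3 repeats this for ITT summaries: "regardless of the subsequent sequence of events regarding study drug exposure".

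Section 11 lists the outputs "along with the analysis population used to generate each TLF". The lead primary safety table, "Summary of Post-treatment Adverse Events for Treatment Period 1 by Treatment", is marked ITT. So is every other primary and secondary safety output, including the aspiration-event summary and listing and the listing of pre-treatment serious events. The safety population is named for none of them.

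SAP Table 2, scenario 1, covers withdrawal after randomisation but before Day 0 therapy. It includes the participant whose marrow sample turns out inadequate, answers no to ITT membership, and has that person followed only until any AEs are closed out.

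**The concern.** AE incidence in Study Period 1 is the primary safety outcome, and the SAP gives two different sets of people for it. The result would depend on which section the programmer follows.

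Neither set fits. Most of the safety outputs are split by treatment or arm, and a screen failure has neither. The ITT set has the more serious gap: it requires an injection, although the intervention begins with an aspiration. Protocol 6.1.5 allows up to four bone punctures for the real procedure, and the sham procedure also breaks the skin. A participant can therefore be exposed to procedural risk, have an AE and still fall outside ITT. Those left out are the people whose Day 0 procedure was not completed, so the omission need not be random with respect to harm.

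**Working it through.** The SAP gives no figure to reproduce on this point. The check compares the sections, follows one participant through them, and then sizes the effect.

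**Side by side**

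| | SAP 4.3 with 4.1.3 | SAP Section 11 with 4.1.2 |
|---|---|---|
| Set used for safety outputs | Safety population | ITT |
| Entry condition | Consent signed | Randomised and first injection given |
| Screen failure | In | Out |
| Real or sham aspiration on Day 0, no injection | In | Out |
| Listed outputs using the safety population | All safety outputs expected | None |

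SAP 4.3 allows departures from its conventions if they are noted in later sub-sections. SAP 7.1.1 notes no change of population. Reading Section 11 as the departure would leave the safety population unused.

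**One participant, followed through the plan.** A person randomised to immediate cell therapy has a real aspiration on Day 0, the sample is inadequate, no injection is given, and an aspiration-site AE occurs.

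1. Table 2, scenario 1: not in ITT; AEs followed to close-out.
2. Section 11, post-treatment AE tables (ITT): absent.
3. Section 11, aspiration-event summary and listing (ITT): absent.
4. SAP 4.2.5 starts the post-treatment period on the day of the first treatment. Protocol 7.2 describes cellular therapy as aspiration plus injection, so Day 0 could qualify. Table 2 places this participant before therapy, so the event could equally be pre-treatment. The text does not settle it.
5. If it is pre-treatment, SAP 7.1.1 promises a listing of pre-treatment AEs, but Section 11 plans one for serious events only, again on ITT. A non-serious event has no listed output, and a serious one is excluded by the label.

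An inadequate sample at Treatment 2 is different: Table 2, scenario 3, keeps that participant in ITT.

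**Size.** Inputs: 20 participants randomised 1:1 (SAP 3.2), so about 10 per arm. The incidence rate is participants with at least one event divided by participants at risk (SAP 7.1.1). The documents give no count of failed aspirations or AEs, so the following are assumptions: *x* injected participants with an AE, and *k* aspirated-only participants, each with an AE.

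- ITT rate = x / 10
- Procedure-started rate = (x + k) / (10 + k)

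| x | k | ITT | Procedure started |
|---|---|---|---|
| 0 | 1 | 0/10 = 0% | 1/11 = 9.1% |
| 4 | 1 | 4/10 = 40% | 5/11 = 45.5% |
| 0 | 2 | 0/10 = 0% | 2/12 = 16.7% |
| 0 | 3 | 0/10 = 0% | 3/13 = 23.1% |

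The table holds the number injected at 10. Protocol 7.6 caps replacement at one participant, so fewer may be injected. If the participant is not replaced in the same arm, x = 0 and k = 1 gives 0/9 against 1/10 (10%).

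**The case against.** The strongest defence is that the harms are not really lost. SAP 7.1.1 draws AEs from all participants and twice promises a listing of pre-treatment AEs, as does Protocol 7.8.2.1. SAP 7.1.2 says that unsuccessful aspirations, and participants who did not tolerate the procedure, will be recorded. Scenario 1 AEs are followed to close-out. On this view the ITT labels in Section 11 are a clerical slip.

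Much of that stands. The events would be collected, and it would be wrong to say that they vanish from the trial. But a record or an unplanned listing is not the primary safety table. The output list that governs production has no place for a non-serious event in such a participant, and it also labels the feasibility outputs ITT.

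Two stronger readings may tempt a reader, and the documents do not support them.

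- *The consented denominator dilutes the AE rates.* This requires people who were never treated to count as at risk of post-treatment events. SAP 7.1.1 leaves the at-risk group undefined, but that is its least natural reading, and no listed safety output uses a consent denominator.
- *A deferred-arm participant who leaves before Treatment 2 stays in the cell column for Period 2.* SAP 4.2.1 starts Study Period 2 on the day of the second treatment, so this person has no Period 2. SAP 7.1.1 also splits Period 1 events by the treatment they followed, and several AE summaries are titled by treatment rather than by arm. What remains is narrower: the as-randomised rule for ITT and these by-treatment splits are not reconciled.

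**Conclusion.** The conflict is real and affects the primary safety outcome. SAP 4.3 and Section 11 name different populations, and the one that Section 11 would use excludes participants exposed to a Day 0 aspiration who were not injected. Their aspiration AEs would be missing from the safety tables.

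A reader might infer that only the cell arm can lose events. That holds for one route: an inadequate sample at Treatment 1 can arise only in the immediate-cell arm, because sham aspiration yields no marrow. A participant who stops after a sham aspiration and before the sham injection is excluded from ITT in the same way.

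The effect depends on such a participant occurring and having an AE. The documents give no frequency for either, and an inadequate sample is not itself a harm. With about 10 per arm, one case moves a rate by about 9 percentage points from zero, or by 5.5 points from 40%. The plan already foresees this participant and the correction is cheap, so it should be made before the analysis is run.

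**What to change.** 1. **SAP 4.1.3:** redefine the safety population as all participants in whom a real or sham aspiration was started, analysed by procedure received.
2. **SAP 4.2.5 and 7.1.1, and Protocol 7.8.2.1:** keep the day-based cut-off. State that the day of first treatment is the day of the first real or sham aspiration, whether or not an injection followed. A cut-off at the moment the procedure starts would be worse. Protocol 6.1.5 gives oral premedication and local anaesthesia beforehand, and a same-day reaction to either could then become pre-treatment. It would also need onset times, which the documents do not show to be collected.
3. **SAP Section 11:** relabel the safety outputs, including the aspiration-event summary and listing, from ITT to this set.
4. **Consented people who had no procedure:** list their AEs separately, without a rate.

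The cost is wording in the SAP and one Protocol section, plus a slightly larger denominator. No new data are needed. Scenario 1 participants have no further assessments, so a footnote should say that their follow-up is shorter. The efficacy analyses stay on ITT.
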